- To evaluate the safety of FMT in MS patients
- To evaluate tolerability of FMT in MS patients

Trial Design:

The proposed randomized, open label, controlled [treatment as usual control group], crossover study will be conducted in 40 patients (n=20 per group) diagnosed with the relapsing forms of multiple sclerosis according to the McDonald 2010 Criteria¹.

Based on the diagnostic criteria patients will be further screened to confirm eligibility and if eligible then consented.

Patients will be randomized 1:1 into two groups. One group will receive FMT, done by rectal enema administered by a RN, at baseline, month 1, month 2, month 3, month 4, and month 5 (early intervention group). The other group will receive treatment as per standard of care (treatment as usual control group) in the beginning of the study. For the last 6 months they will also receive FMT at month 6, month 7, month 8, month 9, month 10, and month 11 (late intervention group).

Clinical visits for both groups will be performed at baseline, and months 1 to 12 inclusive. During these visits a physical exam with vital signs, including a standardized neurological assessment Expanded Disability Status Scale – EDSS) will be done.

Patient's stools will be collected before each FMT procedure in both groups to evaluate gut microbial composition.

Urine will be collected to evaluate gut permeability at baseline, 6 and 12 months for both groups.

Peripheral blood samples also will be collected to evaluate circulating cytokine levels (IL-1 β , IL-2, IL-4, IL-5, IL-6, IL-9, IL-10, IL-12p70, IL-13, IL- 15, IL-17A, IL-17E/IL-25, IL-17F, IL-21, IL-22, IL-23, IL-27, IL-28A, IL-31, IL-33, GM-CSF, IFN γ , MIP-3 α , TNF α and TNF β) at baseline, months 1 to 12 inclusive for both groups.

Peripheral blood samples will also be collected to evaluate blood DNA bacteria at baseline, and months 1 to 12 inclusive for both groups.

Brain MRI with gadolinium [3T MRI machine at Robarts Research Institute] will be performed at baseline, 6 and 12 months for both groups as a safety biomarker [to rule out paradoxical effects; i.e. significant increase in MS activity as defined by Cutter's rule: 5 or more newly enhancing white matter lesions in the brain compared to the previous scan].

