In the event of early termination, a visit will be performed whenever possible, including a final blood sample and all end of treatment assessments that should be completed as soon as possible. All patients with at least 1 week of treatment will be

eligible for analysis.

Number of Patients:

A maximum of 40 patients will be enrolled in intervention part of this study and randomized 1:1 into one of the two groups [20 patients per group] using an internet based randomizer software [<https://www.randomizer.org/>]. We may screen up to an extra 10 patients to compensate for possible drop outs, withdraw consent or those who discontinued for any other reason.

We will also recruit up to 10 healthy volunteers to provide a blood sample [1 tube, 5 ml] to serve as a reference arm for the cytokine analysis. This reference group will be seen only once and will not participate in any other study activities.

Consequently, the total number of participants in this study will be n=50.

Inclusion criteria for patients:

1. Have a confirmed diagnosis of relapsing MS defined by the 2010 Revised McDonald Criteria for the Diagnosis of Multiple Sclerosis¹
2. Have a baseline Expanded Disability Status Scale (EDSS) ≤ 7.0
3. Age equal or older than 18 years of age
4. Be able to attend all clinic appointments without interruption
5. Be proficient in English
6. Be willing and able to give written informed consent
7. Negative blood pregnancy test at screening

Exclusion criteria for patients

1. Not meeting all of the above inclusion criteria
2. Pregnancy [current or planned for the near future] or breastfeeding
3. All qualified patients will not be currently or recently [90 days] treated with immunosuppressive therapy [i.e. chemotherapy] or high dose corticosteroids [i.e. 1g of prednisone or greater or equivalent]. Immune-Modulatory therapies are allowed as per standard of care.
4. Ongoing use of antibiotics
5. Presence of a chronic intestinal disease e.g. celiac, mal-absorption, colonic tumor
6. Concomitant inflammatory diseases
7. Standard of care exclusions for MRI scans as per LHSC standards

Healthy controls Selection:

1. Age equal or older than 18
2. Written informed consent
3. Self reportedly “healthy”, in particular not having a history of any disease or

disorder, or any treatment ever for such [ie lupus, cancer, etc], that in the opinion of the PI could be possibly related to changes in the immune system that would alter the results of a cytokine in blood analysis.

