4. STUDY DESIGN

The proposed randomized, open label, with treat as usual control group, crossover phase II study will be conducted in 40 patients (n=20 per group) with the relapsing forms of multiple sclerosis according to the McDonald 2010 Criteria (Pollman 2011).

Patients will be randomized into 2 intervention groups. One will receive the FMT from baseline and for the first 6 months (early intervention group). On the other hand, the other group will be a control group during the first 6 months and will receive the FMT for the last 6 months of the study (Figure 1). The schedule of study procedures and evaluations for both groups is given in Tables 1 and 2. Patients will be screened for eligibility based on MS diagnosis and EDSS and if eligible then consented. All qualified patients will not be currently or recently treated with high dose steroids.

[figure not shown]

Figure 1. Study Design

At Visit 1, before FMT, patients will be evaluated for their vital signs, medical history and concomitant medications. Also before transplantation, patient's stool will be collected to study their microbial profile, blood analysis to evaluate cytokines levels as well as blood DNA bacteria and finally, urinalysis to assess gut permeability (baseline).

Stool samples for all microbiome analysis will be collected in the form of a used toilet paper packed in a black pouch and transferred in ambient conditions to the laboratory at the Lawson Health Research Institute at St. Joseph's Hospital and stored at -80 °C until the time of DNA extraction.

Peripheral blood will also be collected by standard technique venipuncture by a venipuncture certified and experienced RN. Cytokines levels will be assessed by Luminex in the Department of Microbiology and Immunology at the University of Western Ontario and blood DNA bacteria will be evaluated in St. Joseph Microbiology Laboratory.

For gut permeability patients will be instructed to drink lactulose solution and collect the urine throughout the night and first thing in the morning. A proper collecting bottle will be provided. Once the urine sample bottle reaches the laboratory at St. Joseph's Hospital, London, Ontario the total volume will be measured and an aliquot of 30ml total, 10mL in each sterile urine container (no other additives) will be separated and stored at -20C and sent on dry ice to [name] laboratory at Calgary, Alberta. All biological material will be transported according to biosafety regulations.

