5.2 Patient selection

5.2.1 Patient Inclusion criteria

- Have a confirmed diagnosis of relapsing (relapsing-remitting or secondary progressive) MS defined by the 2010 Revised McDonald Criteria for the Diagnosis of Multiple Sclerosis¹. Any disease duration will be accepted.
- Have a baseline EDSS of = or <7.0
- Older than 18 years of age.
- Be able to attend all clinic appointments without interruption
- Patients must be able to understand English sufficiently well to understand and comply with the clinic and medication schedules and procedures.
- Be willing and able to give written informed consent

- Negative blood pregnancy test at screening

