6.2.1 Screening, Enrolment and Baseline

An informed consent form must be signed prior to initiating any procedures or evaluations for the purpose of the study (**Appendix B**). After the informed consent form has been signed patients will be randomized to receive FMT for the first 6 months of the study or to be a standard per treatment control group that will received treatment at the last 6 months of the study.

The following evaluations at baseline visit and prior to FMT will be performed in both groups:

- Medical history;
- Vital signs (including pulse, respiration rate, blood pressure and temperature);
- Physical Exam (including weight in kg);
- Concomitant medications;
- Dietary history;

- Expanded Disability Status Score (EDSS);
- Blood samples will be taken for haematology (including haemoglobin, red blood cell count, white blood cell count, differential and platelets);
- Blood samples will be taken for serum chemistry (sodium, potassium, chloride, uric acid, creatinine, blood urea nitrogen, total protein, calcium, albumin, total bilirubin, AST, ALT, alkaline phosphatase, glucose);
- Blood sample for multiplex cytokine profiling (includes pro-inflammatory (IL-6, IL-15, IL-17, GM-CSF, TNF α) and anti-inflammatory (IL-4, IL-10 and IL-14) cytokines).
- Clean catch, mid-stream urine for urinalysis and micro analysis (including pH, protein, glucose, ketones, nitrites, leukocyte esterase, RBCs, WBCs) and gut permeability;
- Blood sample for blood bacterial DNA
- Head MRI as baseline

After evaluation, the FMT via rectal enema will be performed by a RN in each visit.

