11.3 Patient Information and Consent

Patients attending a clinic specializing in the care of patients with MS will be approached by their Physician or nurse regarding their interest in participation. If they express interest and consent they will then meet with the investigator and his representative. At this time, the patient will be questioned regarding inclusion and exclusion criteria, and if eligible will request informed consent for participation. The consent will contain all the essential elements of informed consent set forth in ICH E6. The investigator or his/her representative will explain the nature of the study to the patient, and answer all questions regarding this study. The informed consent must be reviewed, signed and dated by the patient and the person administering the consent prior to screening the patient for the study. A copy of the informed consent form will be given to the patient and the original will be placed in the patient's medical record if in accordance with the institution's standard operating procedures. An entry must also be made in the patient's chart to confirm that informed consent was obtained prior to any study-related procedures and that the patient received a signed copy. To protect the confidentiality of the patient, all reports and communications relating to the study will identify patients by assigned patient identifier only. Potential donors will be recruited from student groups or staff volunteers in Western University.

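### Randomisation is placed before the baseline measures in an open-label trial, and criteria that need a study measurement have no assured place before allocation

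*Combined protocol and SAP*

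**What the plan says.** **Randomisation and baseline.** Section 6.2.1 opens with the rule that "An informed consent form must be signed prior to initiating any procedures or evaluations for the purpose of the study". It continues: "After the informed consent form has been signed patients will be randomized to receive FMT for the first 6 months of the study", or to the control group treated later. The list of baseline measures comes next, introduced by "The following evaluations at baseline visit and prior to FMT will be performed in both groups". That list includes medical history, concomitant medications, EDSS, blood for cytokines and bacterial DNA, urine and head MRI.

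**Schedule.** In Tables 1 and 2 the only procedure at the pre-visit is informed consent. Every measurement starts at the Baseline visit, which is planned at 1.5 hours for the early group and 45 minutes for the late group.

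**Eligibility.** The synopsis (Trial Design) says "Based on the diagnostic criteria patients will be further screened to confirm eligibility and if eligible then consented". Section 4 says "Patients will be screened for eligibility based on MS diagnosis and EDSS and if eligible then consented". Section 11.3 says "At this time, the patient will be questioned regarding inclusion and exclusion criteria, and if eligible will request informed consent for participation", but further on it requires the consent form to be signed before the patient is screened. Section 4.2 mentions screening and then randomisation, with the start of FMT as the only time anchor.

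**Criteria.** Section 5.2.1 includes "Have a baseline EDSS of = or <7.0" and a negative blood pregnancy test at screening. Section 5.2.2 has an MRI technologist check compatibility, at no stated time.

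**Allocation.** The trial is open label, with 40 patients in two groups of 20. The synopsis (Number of Patients) says they are allocated "using an internet based randomizer software". No section says when, or to whom, the assignment is revealed.

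**The concern.** In an open-label trial, the moment of randomisation is the last point at which staff and patient can be unaware of the arm. Anything measured afterwards can be influenced by knowing it. Two things are at stake.

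- **Baseline values.** If EDSS and histories are recorded after allocation, the reference for later comparison is collected with the arm known. Section 3.2 uses EDSS to look for paradoxical worsening, so a baseline score shaded in one arm would shift that arm's apparent change.
- **Who contributes data.** A patient who is allocated and then withdraws, or is found not to meet a criterion, before the baseline samples are taken has no baseline cytokine value. Section 7.0 defines the cytokine outcome as change from baseline. Only one group learns at allocation that its FMT is six months away, so the loss need not be equal between arms.

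**Working it through.** The plan gives no figure on this point to reproduce. The check is to set out the order of events in each place and see what is fixed.

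**Step 1. Order by section**

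| Place | Order given |
|---|---|
| Synopsis, Trial Design | eligibility screening, consent; randomisation in the paragraph that follows |
| Section 4 | screening on MS diagnosis and EDSS, consent; randomisation not placed relative to these |
| Section 4.2 | screening and randomisation, anchored only to the start of FMT |
| Section 6.2.1 | consent before any study evaluation; consent, randomisation, baseline list |
| Section 11.3 | questioning on the criteria, consent, screening |

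An eligibility check before consent appears in three places (synopsis, Section 4, Section 11.3). These do not sit easily with Section 6.2.1, which allows no study evaluation before consent, or with the later sentence in Section 11.3 that puts screening after consent.

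**Step 2. Where the baseline measures fall**

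- Section 6.2.1 names randomisation first and then describes evaluations in groups that already exist.
- Section 6.2.1 and the Visit 1 text in Section 4 time these evaluations against FMT only. No section requires them to be finished before randomisation or before the arm is disclosed.
- The pre-visit holds consent alone, so no baseline measure is scheduled there.
- The Baseline visit is planned at 1.5 hours (90 minutes) in one arm and 45 minutes in the other, a difference of 90 − 45 = 45 minutes. A visit with a different planned length by arm fits an arm that is already known.

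**Step 3. Criteria that questioning cannot settle**

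- *EDSS.* Section 5.2.1 sets the limit on the baseline EDSS. Section 4 and Section 6.2.1 both list EDSS among the baseline assessments, although Section 4 also names EDSS in the check before consent.
- *Blood pregnancy test.* It is required at screening, but neither table has a row for it, and Section 4 lists a pregnancy test among the baseline assessments.
- *MRI compatibility.* The technologist's check has no time attached.

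The antibiotic, steroid and immunosuppressant exclusions differ: the questioning in Section 11.3 can reasonably cover them before consent.

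**Step 4. What follows for the outcomes**

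- *EDSS:* a rater's judgement, so exposed to knowledge of the arm.
- *Cytokines:* assayed by Luminex in duplicate (Section 6.2.3), so less exposed. The main route to bias is differential loss of patients.
- *Loss:* with 20 per group, each patient lost before baseline is 1/20 = 5% of an arm. Section 9.6 rules out imputation, so a missing baseline stays missing.

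The documents give no rate of loss between allocation and baseline. The allowance of up to 10 extra screened patients (synopsis) and the 90% adherence target (Section 5.4) cover the whole trial and do not isolate that interval.

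**The case against.** **The text does not state outright that baseline follows allocation.** Placing randomisation after consent sets only an earliest time. A site could do the assessments first, allocate part-way through the Baseline visit, and then give FMT to the early group. That would also produce visits of different length, so the tables support the reading in Step 2 without proving it. This stands as a limit on certainty. However, nothing in the plan asks a site to work that way, and the written order points the other way.

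**Eligibility is checked early.** A reader might infer that patients are randomised before any eligibility check and that eligibility is decided with the arm known. The documents do not support this: three places put a check before consent, and Section 4 names EDSS in it. Patients come from a specialist MS clinic, so diagnosis and history are probably well known. What remains is narrower: the study's own baseline EDSS, the blood pregnancy test and the MRI check.

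**The trial is open label throughout.** Every later EDSS is also scored with the arm known, so an unmasked baseline score adds only modestly to the bias in a safety measure. This is fair. Even so, the baseline is the one assessment that an open-label trial can obtain before the arm exists, and the plan gives that up for no benefit.

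**Both arms are promised FMT.** This may keep late-group patients in the trial. Unequal loss is therefore a risk and not a prediction.

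**Conclusion.** The point holds in a limited form. As written, the plan allocates after consent and collects baseline EDSS, histories and samples afterwards with no masking, and nothing in the documents prevents this. Criteria that need a study measurement or check have no assured place before allocation, and the sections disagree on the order of screening and consent.

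The consequence is greatest for EDSS. For the primary cytokine outcome, bias in the measurements themselves is not shown; the main risk is missing baseline values, possibly unequal between arms.

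The size cannot be estimated. A reader might assume that 10 to 20% of those allocated are lost, which is 0.10 × 40 = 4 to 0.20 × 40 = 8 patients, but no passage supplies such a rate. Nor does use of a web randomiser show that allocation is unconcealed: the plan is silent on when and to whom assignments are revealed.

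The conclusion rests on reading Section 6.2.1 in its written order. It is a correction worth making because it is cheap, and it does not invalidate the randomisation itself.

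**What to change.** State one sequence and use it in the synopsis, Section 4, Section 4.2, Section 6.2.1 and Section 11.3:

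1. consent;
2. screening, with every eligibility criterion confirmed and recorded;
3. baseline EDSS, samples and MRI completed;
4. randomisation as the last step.

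Any informal questioning before consent can be described as pre-screening. Add that the assignment is not revealed to enrolling staff until baseline is complete. Amend Tables 1 and 2 so that the measurement-based eligibility items and the point of randomisation each have a stated place.

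**Cost.** Modest rescheduling. The pre-visit is already planned at 1.5 hours with only consent listed, so some of the baseline measures could move there. FMT availability and the length of the following visit would have to be arranged once the arm is known. No extra patients or assays are needed.

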3.1 Primary outcome

To evaluate if FMT from healthy donors can significantly change cytokine profile in peripheral blood samples of RMS patients.

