6.2.3 Peripheral blood cytokines levels

Cytokine levels will be measured as previously described⁷². Peripheral blood will be collected into EDTA blood collection tubes ensuring complete mixing with anticoagulant to avoid clotting. Within 60 minutes of blood collection samples will be spun for 10 minutes at 4500xg. The plasma will be collected and aliquoted into cryovials. All samples will be collected and stored at -80°C before the plasma is measured for 25 immunological cytokines using a luminex-based multiplexed immunoassay. The Human Th17 Magnetic bead panel (HTH17MAG-14K, Millipore) will be used in this study to detect changes in Interleukin 1 β (IL-1 β), IL-2, IL-4, IL-5, IL-6, IL-9, IL-10, IL-12p70, IL-13, IL-15, IL-17A, IL-17E/IL-25, IL-17F, IL-21, IL-22, IL-23, IL-27, IL-28A, IL-31, IL-33, granulocyte macrophage colony stimulating factor (GM-CSF), interferon γ (IFN γ), macrophage inflammatory protein 3 α (MIP-3 α), tumour necrosis factor α (TNF α) and TNF β . Plasma samples will be run in duplicate and assays will be standardized as per product specifications. Plasma cytokine levels in healthy controls will be compared to levels in MS patients at all time points. Moreover, cytokine levels of MS patients at baseline (D0) will be compared to levels at 12 months to determine whether intervention (FMT) had an effect on pro- and anti-inflammatory cytokine levels.

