6.3 Sample Size analysis

It was assumed that the acceptable Type I error will be 0.05 and power will be 0.8. Moderate effect size effect is expected. This is a study of a kind that has never been done before in this population. From similar studies in other populations or other interventions on a similar population, a 40% change in cytokine levels (ie TGFbeta1) analysis is expected, as reported on other cytokine study with no pharmacological intervention, such as vitamin D supplementation⁷³.

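### The visit sections name IL-14 and an unqualified IL-17 in the cytokine profile, but the only panel described has no IL-14 and three IL-17 forms, and no section says which analytes are primary

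*Combined protocol and SAP*

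**What the plan says.** **Primary outcome (3.1).** The question is whether FMT "can significantly change cytokine profile in peripheral blood samples of RMS patients". No analyte is named.

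**Visit sections (6.2.1 and 6.2.2).** Both call for "multiplex cytokine profiling (includes pro-inflammatory (IL-6, IL-15, IL-17, GM-CSF" and TNF-alpha on the pro-inflammatory side, followed by "anti-inflammatory (IL-4, IL-10 and IL-14) cytokines". The same eight names appear at baseline and at all later visits.

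**Assay section (6.2.3).** Plasma is to be "measured for 25 immunological cytokines using a luminex-based multiplexed immunoassay". A single kit is given: "The Human Th17 Magnetic bead panel (HTH17MAG-14K, Millipore) will be used in this study to detect changes in" 25 named analytes. The synopsis repeats the same 25 under the trial design and again under the criteria for evaluation. Section 4 likewise says "Cytokines levels will be assessed by Luminex". No other cytokine assay is described.

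**Analysis (9.3).** A mixed-design ANOVA is specified for biomarkers, with no list of cytokines, no composite and no multiplicity rule.

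**Sample size (6.3 and 9.1).** Section 6.3 states that "a 40% change in cytokine levels (ie TGFbeta1) analysis is expected". Section 9.1 says the group size was chosen arbitrarily, as a convenience sample.

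**The concern.** The visit sections and the assay section describe the same measurement and disagree on its content. One cytokine said to be profiled at every visit has no assay behind it. Another is named in a way that fits three different measured analytes.

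This matters because the cytokine profile is the primary outcome. Section 6.2.3 frames the question as the effect of FMT on pro- and anti-inflammatory levels, and the visit sections are the only place that assigns analytes to those two groups for this trial. One of the three names in the anti-inflammatory group will have no data under the plan as written.

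The primary family is also left open. Section 3.1 names no analytes and 9.3 does not choose any. In an open-label trial with monthly cytokine samples, that leaves room to decide after seeing the results which cytokines carry the primary conclusion.

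**Working it through.** **Inputs.** The eight names come from 6.2.1 and 6.2.2. The 25 analytes come from 6.2.3 and both synopsis lists.

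**Step 1: reproduce the plan's own count.** The analytes in 6.2.3 are IL-1β, IL-2, IL-4, IL-5, IL-6, IL-9, IL-10, IL-12p70, IL-13, IL-15, IL-17A, IL-17E/IL-25, IL-17F, IL-21, IL-22, IL-23, IL-27, IL-28A, IL-31, IL-33, GM-CSF, IFNγ, MIP-3α, TNFα and TNFβ. Counting IL-17E/IL-25 as one, there are 25. The stated figure is reproduced.

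**Step 2: match the eight names to the panel.**

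| Name in 6.2.1 and 6.2.2 | On the panel in 6.2.3? |
|---|---|
| IL-6 | Yes |
| IL-15 | Yes |
| GM-CSF | Yes |
| TNF-alpha | Yes |
| IL-4 | Yes |
| IL-10 | Yes |
| IL-17 | Ambiguous: IL-17A, IL-17E/IL-25 or IL-17F |
| IL-14 | No |

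- Exact matches: 6 of 8.
- Measurable analytes if one IL-17 form is meant: 6 + 1 = 7.
- Measurable analytes if all three forms are meant: 6 + 3 = 9.
- Panel analytes not named in the visit sections even on the wider reading: 25 − 9 = 16.

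**Step 3: check the cytokine cited in 6.3.** TGF-beta1 is not among the 25.

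**Step 4: show why the size of the family matters.** This is an illustration and not a figure from the plan. Assume each analyte is tested once at 0.05, with no true effects and independent tests. The chance of at least one false positive is 1 − 0.95^k.

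| Analytes tested (k) | Calculation | Chance of at least one false positive |
|---|---|---|
| 7 | 1 − 0.95^7 | about 30% |
| 9 | 1 − 0.95^9 | about 37% |
| 25 | 1 − 0.95^25 | about 72% |

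Cytokines measured in the same plasma sample are probably positively correlated, which would lower these figures. The documents give no correlations, so I cannot say by how much.

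**The case against.** The strongest reply is that the visit lists are illustrative. They are introduced as things the profiling includes, they sit in procedure checklists, and nothing labels them primary. The full list of 25 is identical in all three places that set out what is measured or evaluated, and 6.2.3 states the number. On this view the 25 govern and the eight are loose examples.

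Much of that stands. A reader might infer that the protocol has two competing primary sets, one of eight and one of 25. The documents do not support this, because the wording of 6.2.1 and 6.2.2 is not exhaustive and no section calls the eight primary. Nor can one say that a designated primary analyte is lost: IL-14 matters only as a named part of the profile that is the primary outcome.

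The reply does not dispose of IL-14 or IL-17. An example of what a panel includes must be on the panel, and IL-14 is not. The documents do not show whether it is a typing error for another analyte.

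A second fair reply is that the freedom to select among analytes comes mainly from the silence of 3.1 and 9.3, and would remain if IL-14 were deleted. I agree. The mismatch adds to that gap but does not create it.

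A third is that TGF-beta1 has little consequence. A reader might infer that the sample size rests on an unmeasured cytokine. It does not: 6.3 gives no standard deviation and derives no number, and 9.1 says the group size was arbitrary.

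**Conclusion.** The point holds as an internal inconsistency in the description of the primary outcome. Of eight named cytokines, six match the panel, one is ambiguous among three analytes, and one is not on the panel. The last statement means not measurable with the panel as the protocol lists it; it rests on 6.2.3 being the complete description of the cytokine assay, and no section suggests another.

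Alongside this, no section defines which analytes make up the primary family. The false-positive figures show that the choice of family matters, but they depend on independence and on one test per analyte, so they are illustrative only.

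The stored plasma and the panel data remain usable. What is at risk is how the primary result is read, so this should be settled before analysis. It does not invalidate the design, and it does not show that the visit-section subset has to be the primary family. The TGF-beta1 reference is a minor side point.

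**What to change.** 1. Use one cytokine list in both synopsis entries and in 6.2.1, 6.2.2 and 6.2.3. The simplest way is to remove or correct IL-14 in the two visit sections and refer there to 6.2.3. If IL-14 is truly wanted, name the assay for it.
2. State which IL-17 form or forms are meant.
3. In 3.1 and 9.3, state which measured analytes are primary: either a named subset, or all 25 with a stated method of multiplicity control. Treat any others as exploratory. Do this before any analysis, including the interim analysis mentioned in 12.3.
4. In 6.3, either label the 40% change in TGF-beta1 as an external illustration or tie the expected change to a measured analyte, noting that the group size does not depend on it.

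Items 1, 2 and 4 are wording and need no new sample or visit; only keeping IL-14 would require an extra assay. Item 3 is a real decision about the endpoint. Its cost is that a stated hierarchy limits which cytokines can support the primary conclusion, and controlling for all 25 lowers power for each one.
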